11.3.2 Sample Size

Based on the data from previous cross-sectional studies (42, 50), we assume that the baseline COST score follows a normal distribution with the mean 25 and the standard deviation 12 and the 12-month FU score follows a normal distribution with the mean 22.5 and the standard deviation 12. Thus, the effect size of change is assumed to be 10%. The correlation between the baseline and the 12-month FU scores is assumed to be 0.2. Based on these assumptions, a sample size of 394 cancer patients will be needed to achieve a 90% power to detect the 2.5 difference (i.e., 10% change) at the 0.05 significance level using a two-sided Wilcoxon Signed-rank Test. These results are based on 20,000 Monte Carlo samples for the sample distributions under the null and the alternative hypothesis. The sample size will be 296 if the power remains at 0.90 and the correlation is assumed to be 0.4. A pilot study assessing financial burden among patients with advanced cancers had a 24% attrition rate between baseline and 12 month assessments, excluding those who died before the 12 month time point (36). An ongoing study on employment among cancer patients across the stage spectrum had a 30% attrition rate at the 12month follow-up ([name], personal communication). Therefore, we assume a 30% attrition rate at the 12-month follow-up and expect to enroll 563 patients into the study. Note: The imputation was based

on Monte Carlo samples in simulations, which caused slight fluctuations in the sample size. However, with 20,000 simulations, the fluctuation rate is only about 1%.

With these sample sizes, we will have the power of 1.0 to detect a difference of 5 (i.e., 20% change) from the baseline to the 24-month FU score, while the latter is assumed to follow a normal distribution with mean 20 and standard deviation 12. The above computations were done using PASS 14 (83).

Table 4: Power A	nalysis. Power:	0.80 and 0.90.	Correlation:	0.20 and 0.40.
------------------	-----------------	----------------	--------------	----------------

Power 0.797 (0.006) [0.791	N 292 0.802]	H0 Diff0 0.0	H1 Diff1 2.5	Corr R 0.200	Target Alpha 0.050	Actual Alpha 0.050 (0.003) [0.047	Beta 0.203 0.053]
0.803 (0.006) [0.798	218 0.809]	0.0	2.5	0.400	0.050	0.049 (0.003) [0.046	0.197 0.052]
0.900 (0.004) [0.896	394 0.904]	0.0	2.5	0.200	0.050	0.051 (0.003) [0.048	0.100 0.054]
0.904 (0.004) [0.900	296 0.908]	0.0	2.5	0.400	0.050	0.051 (0.003) [0.048	0.096 0.054]

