11.4 Statistical Analysis Plan

11.4.1 Primary Objective

The primary aim is to evaluate the change in the level of self-reported financial burden from baseline (within 60 days of diagnosis) to 12 months after diagnosis of colon or rectal cancer treated with curative-intent.

We will calculate the difference of COST measurements from baseline to 12-month FU for the completers who provide data at both time points, and use the paired t-test to assess if the mean difference is significantly different from zero. In case the data are not normally distributed, nonparametric methods (e.g., Wilcoxon signed-rank test) will be used instead to assess the difference. For the participants with missing measurements at one time point, we will implement the methods as described in Section 11.4.3 to handle the missing values. The two results will be compared as a sensitivity analysis.

In addition, linear regression models with the change of COST from baseline to 12-month FU as the response variable will be fit to investigate the impact of other factors, including demographics variables (e.g., age, sex, marital status), clinical variables (e.g., stage of disease, malignancy type, chemotherapy status), baseline questionnaire variables (e.g., self-efficacy,). The three-level treatment status (IV chemotherapy, chemotherapy without IV, and no chemotherapy) will also be evaluated as a predictor. The impact of system level variables (including being designated a minority/underserved site or not, availability of financial resources for patients) will be examined in the regressions as well. Since pregnant women may have higher health-care related costs, the response will be compared between pregnant women and the others; if significant, the subset analysis may be performed in this population.

- 11.4.2 Secondary Objectives
 - 11.4.2.1 Evaluate reported access and utilization of financial services (i.e. financial counselor, navigator, social workers) and its association to financial burden in the first 12 months after diagnosis of colon or rectal cancer treated with curative-intent.

The 8-question CCVI measure as described in Section 7.1.2 will be analyzed to evaluate the change from

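### The primary test changes from paired t to an unspecified nonparametric method if the data look non-normal, so the primary hypothesis is settled only after the data are seen

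*Combined protocol and SAP*

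**What the plan says.** Section 11.4.1 takes completers with COST at baseline and 12 months and will "use the paired t-test to assess if the mean difference is significantly different from zero". The next sentence allows a replacement: "In case the data are not normally distributed, nonparametric methods (e.g., Wilcoxon signed-rank test) will be used instead to assess the difference". It does not say how normality will be judged, at what threshold, or on which variable (the two scores or their difference). The Wilcoxon test is given only as an example.

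Section 11.3.2 leads with the other test. Its 394 evaluable patients are for a comparison "at the 0.05 significance level using a two-sided Wilcoxon Signed-rank Test", with both scores assumed normal.

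Nothing else in the document fixes one primary test. The sensitivity comparison in 11.4.1 sets completers against the missing-data methods of 11.4.3; it does not set t against Wilcoxon. The same switch appears for the secondary measures in 11.4.2.1 and 11.4.2.2. Sections 11.4.2.3 and 11.4.2.5 carry the primary approach over to other time points and to the alternate burden measures.

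**The concern.** The two tests answer the same question only when changes are symmetric. The t-test asks whether the mean change is zero. The signed-rank test asks whether changes are symmetric about zero, which in practice concerns their pseudomedian. Skewness is one of the things that would trigger the switch, and it is also the condition under which the two nulls separate.

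Skew is plausible here: a minority may take a heavy financial hit while most patients change little. The pseudomedian then lies above the mean. The signed-rank test can reject when the mean change is zero, and it loses power to detect a mean decline. The t-test needs no rescue at this sample size, so the switch buys no protection for the mean. Because the check and the replacement are both open, the choice would also be made with the results in view.

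**Working it through.** **Inputs from section 11.3.2.** Baseline COST is normal with mean 25 and SD 12. The 12-month score "follows a normal distribution with the mean 22.5 and the standard deviation 12". "The correlation between the baseline and the 12-month FU scores is assumed to be 0.2". Two-sided alpha is 0.05, power 90%, evaluable N 394, attrition 30%. Section 7.1.1.1 gives the score range as 0–44.

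**Assumptions, not in the documents.** Normality is judged by Shapiro-Wilk at 0.05, with Wilcoxon used if it rejects and the paired t-test otherwise. The shape of the change is varied as shown below.

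**Step 1: reproduce the plan.**
- SD of change = 12 × √(2 × (1 − 0.2)) = 15.18.
- Simulated Wilcoxon power at N = 394 for a 2.5-point difference (20,000 samples) is 0.890, against 0.900 stated. This is close enough to count as reproduced. The other rows of Table 4 come out similarly: 0.787 for 0.797, 0.787 for 0.803, 0.892 for 0.904.
- Paired t-test at N = 394: power 0.903 by noncentral t, 0.902 by simulation. Closed form: N = (15.18 × (1.960 + 1.282) / 2.5)², about 388.
- 394 / 0.70 = 562.9, so 563 enrolled.

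**Step 2: is the t-test safe without normality?** With N = 394, true mean change 0, SD 15.18 and shifted-gamma changes of skewness −0.25 to −2, the t-test alone rejects in 4.5% to 5.7% of 4,000 simulated trials per scenario (Monte Carlo SE about 0.35 points). It holds its level.

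**Step 3: the switching rule at the plan's SD.** Let 20% of patients lose L points and let the rest gain enough to make the mean zero: 0.2 × L / 0.8, which is 4.5 for L = 18 and 3.5 for L = 14. The gap between groups is g = 22.5 or 17.5. Holding total SD at 15.18, the within-group SD is √(230.4 − 0.16 g²), which is 12.2 or 13.5. Skewness is −0.2 × 0.8 × 0.6 × g³ / 15.18³, which is −0.31 or −0.15.

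| Pattern, mean change 0 | Skewness | Switching rule | t-test alone |
|---|---|---|---|
| 14-point loss | −0.15 | 5.7–5.8% | 5.1% |
| 18-point loss | −0.31 | 9.1% | 5.3% |

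If 14 and 18 points are read as the gap between the groups instead, the rule gives 5.2–5.7%.

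**Step 4: bounded scores.** With scores rounded and clipped to 0–44, so that the mean change is only approximately zero, the same patterns give 5.1% and 6.0% at correlation 0.2, and 5.6% and 7.8% at 0.4. In the 7.8% run the t-test itself gave 6.6%.

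**Step 5: power for a mean change of −2.5 at SD 15.18.** Shifting the whole 18-point pattern down by 2.5 gives 0.78 for the switching rule against 0.91 for the t-test. Keeping the 18-point loss and setting the others' gain so that the mean is −2.5 gives 0.85 against 0.91. The 14-point patterns reach up to about 0.90.

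**Step 6: where the effect vanishes or grows.**
- Symmetric changes: 4.9% (heavy-tailed t with 5 df) and 5.1% (bounded score), so no inflation.
- Shifted-gamma changes at SD 15.18: 6.6% at skewness −0.25, 12.6% at −0.5, 37.7% at −1. The check triggers the switch in 42% of trials at −0.25 and in at least 95% from −0.5.
- A mixture in which 15% of patients drop 15 points (skewness −0.46) gives 14.0%, but its SD of change is 10.2, well below 15.18.

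**The case against.** The strongest reply is that the endpoint, in sections 2.1.1 and 11.2, is simply the change in COST; the mean enters only in the t-test sentence. The Wilcoxon test keeps 5% for its own null, so it is not invalid. That stands. The fault is that the target is not fixed, and the figures above measure error only against the mean difference that 11.4.1 names.

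The consequence is also limited. This is a single-arm observational cohort, and mean-based analyses remain planned: regression on the change in COST in 11.4.1 and a mixed model in 11.4.2.3. These soften the harm but do not say which test is primary.

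A reader might infer gross inflation, 14% or far more. The documents do not support that. Such figures need skewness of about −0.5 or beyond, or an SD of change below the plan's 15.18, or a correlation outside its 0.2–0.4: with bounded scores, about 14% returned only for the 18-point pattern at correlation 0.7. The bound works against large losses as well. At mean 25 and SD 12, (18 − 25)/12 = −0.58, so more than a quarter of patients start below 18 and cannot lose 18 points.

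A reader might also infer that the sample size is wrong because it rests on the test that is not first choice. It is not wrong: the stated power reproduces, and 394 pairs give the t-test its 0.90.

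**Conclusion.** The point holds as a defect of specification with a modest numerical effect. The primary hypothesis depends on an undefined look at the data, sections 11.3.2 and 11.4.1 lead with different tests, and the switch gives the mean no protection that the t-test lacks at about 394 pairs.

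On the assumed check and loss patterns, the cost at the plan's own SD runs from nothing to about 4 points of type I error, and from almost nothing to about 0.13 of power (0.91 − 0.78). The true size cannot be known from the documents, which give neither the skewness of change nor the normality check. The change is worth making because it costs nothing, not because the expected error is large.

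**What to change.** In section 11.4.1, name the paired t-test with a 95% confidence interval for the mean COST change as the single primary analysis, whatever the distribution looks like. Report the Wilcoxon signed-rank test as a sensitivity analysis, with a note that it addresses a different null when changes are skewed. Remove the conditional replacement.

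In section 11.3.2, restate the calculation for the paired t-test: 394 pairs, SD of change 15.18, difference 2.5, power 0.90. Apply the same rule where the switch or the primary approach is reused in 11.4.2.

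The cost is a few sentences. The 394 evaluable and 563 enrolled patients are unchanged, and no further data are needed.

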1.2.6 Description of the Patient Population and Assessment Time Points in Proposed Study

This study will focus on patients receiving curative-intent treatment for colon or rectal cancer specifically for several reasons. Colon and rectal cancer were chosen because these are common malignancies that are most frequently diagnosed in the curative-intent setting (45). Because these patients typically have longer survival than those with metastatic disease, they potentially have a longer period of time to be impacted by the costs of their cancer and changes in employment. Previous studies have largely focused only on patients receiving chemotherapy and/or with metastatic disease (18, 42, 46). The recently opened SWOG trial investigating financial burden (PI: [name]) focuses on metastatic disease, and our proposed study of early stage disease will synergize with her work and will contain some common variables to allow for cross-study analysis.

There remain many unanswered questions about the financial burden that our study will address. We hypothesize that those who receive chemotherapy may have higher burden than those who do not, however this is currently unknown and will be prospectively studied in this study. We will stratify by both disease type and receipt of chemotherapy to allow for robust comparisons between these groups, which has not been previously reported in a prospective study. These comparisons may be important as we develop implementation studies and education to focus on malignancy types and treatment settings that demonstrate the highest level of burden.

We chose the time points, baseline at diagnosis, 3, 6, 12, and 24 months because they correlate with important landmarks in the treatment of colorectal cancer. At three months after diagnosis, most patients are in the initial phase of their therapy (either surgery for colon cancer or chemo-radiation for rectal). By 6 months, most patients are approaching the end of their planned therapy, and by 12 months most patients are typically done with therapy. The 24 month time point is an opportunity to collect data related to adherence to follow-up guidelines, more specifically either a colonoscopy, sigmoidoscopy, or barium enema. By analyzing data at each of these time points, there is hope to gain better understanding of the timing of changes in employment and financial burden to inform when in the cancer continuum would a future intervention be optimal.

2. Objectives

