5.6 Additional Requirements

- 5.6.1 Patients must provide a signed and dated, written informed consent form.
 - **NOTE:** Copies of the consent are not collected by the ECOG-ACRIN Operations Office Boston.
- 5.6.2 Data collection for this study will be done exclusively through the Medidata Rave clinical data management system and the EASEE-PRO system. Access to the trial in Rave is granted through the iMedidata application to all persons with the appropriate roles assigned in Regulatory Support System (RSS). To access Rave via iMedidata, the site user must have an active CTEP-IAM account (check at <https://ctepcore.nci.nih.gov/iam/>) and the appropriate Rave role (Rave CRA, Read-Only, CRA, Lab Admin, SLA or Site Investigator) on either the LPO or participating organization roster at the enrolling site. To the hold Rave CRA role or CRA Lab Admin role, the user must hold a minimum of an AP registration type. To hold the Rave Site Investigator role, the individual must be registered as an NPIVR or IVR. Associates can hold read-only roles in Rave.

Upon initial site registration approval for the study in RSS, all persons with Rave roles assigned on the appropriate roster will be sent a study invitation e-mail from iMedidata. To accept the invitation, site users must log into the Select Login (https://login.imedidata.com/selectlogin) using their CTEP-IAM user name and password, and click on the "accept" link in the upper right-corner of the iMedidata page. Please note, site users will not be able to access the study in Rave until all required Medidata and study specific trainings are completed. Trainings will be in the form of electronic learnings (eLearnings), and can be accessed by clicking on the link in the upper right pane of the iMedidata screen.

Users that have not previously activated their iMedidata/Rave account at the time of initial site registration approval for the study in RSS will also receive a separate invitation from iMedidata to activate their account. Account activation instructions are located on the CTSU website, Rave tab under the Rave resource materials (Medidata Account Activation and Study Invitation Acceptance). Additional information on iMedidata/Rave is available on the CTSU members' website under the Rave tab at www.ctsu.org/RAVE/ or by contacting the CTSU Help Desk at [name] or by e-mail at [contact].

6. Methodology Plan

- 6.1 This is a single arm, prospective, longitudinal cohort study.
- 6.2 Setting

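### Section 11.4.1 does not specify baseline COST as a covariate in the supplementary regressions of 12-month COST change, at a cost in precision of 43% to 67% more residual variance on the plan's own correlations

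*Combined protocol and SAP*

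**What the plan says.** After the primary paired comparison, Section 11.4.1 adds that "linear regression models with the change of COST from baseline to 12-month FU as the response variable will be fit". The predictors are demographics, "clinical variables (e.g., stage of disease, malignancy type, chemotherapy status), baseline questionnaire variables (e.g., self-efficacy" and the like, and system-level variables such as minority/underserved site status. It continues: "The three-level treatment status (IV chemotherapy, chemotherapy without IV, and no chemotherapy) will also be evaluated as a predictor". Baseline COST is not named in this list, and no other section names it as a covariate for this model.

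Section 11.3.2 sizes the study on a normally distributed baseline COST (mean 25, SD 12). For the later visit it assumes that "the 12-month FU score follows a normal distribution with the mean 22.5 and the standard deviation 12". For the link between visits, "The correlation between the baseline and the 12-month FU scores is assumed to be 0.2", with 0.4 as an alternative.

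The between-group interest is in Section 1.2.6: "We hypothesize that those who receive chemotherapy may have higher burden than those who do not". Section 6.1 gives the design: "This is a single arm, prospective, longitudinal cohort study". Chemotherapy is therefore an observed exposure, not an allocated one.

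**The concern.** A change score contains the baseline value with a negative sign. When the correlation between visits is low, much of the variation in change is variation in where patients started. A regression that leaves baseline out keeps that variation as noise, although Section 11.4.1 can only compute a change for patients who have a baseline score.

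Two things are at stake. The first is precision for all the predictor analyses, including chemotherapy status. The second is interpretation: if the chemotherapy groups start at different COST levels, the unadjusted and adjusted models give different contrasts. A plan that does not name its model leaves that choice to be made after the data are seen.

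**Working it through.** **Inputs.** From Section 11.3.2: SD 12 at both visits; correlation r = 0.2 (used for sizing) or 0.4; target change 2.5 points; two-sided alpha 0.05; 90% power; 394 completers; 30% attrition; 563 enrolled. From Section 11.3.1: chemotherapy and no-chemotherapy groups roughly equal. Assumed here: no other covariates in the model.

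**1. Reproduce the plan's figure.** Var(change) = 2 × 12² × (1 − 0.2) = 230.4. Then n = (1.960 + 1.282)² × 230.4 / 2.5² = 388, or 390 with the exact t calculation, against 394 stated. A 20,000-run simulation of the signed-rank test at 394 gives power 0.894 against 0.900 stated. Enrolment is 394 / 0.70 = 562.9, so 563. At r = 0.4 the formulas give 291 to 293 against 296. The plan's sizing is sound on its inputs.

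**2. Residual variance with and without baseline COST.** Without: 2σ²(1 − r). With: σ²(1 − r²). The ratio is 2/(1 + r).

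| r | Without | With | Variance ratio | SE ratio |
|---|---|---|---|---|
| 0.2 | 230.4 | 138.24 | 1.667 | 1.29 |
| 0.4 | 172.8 | 120.96 | 1.429 | 1.20 |

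Naming baseline COST removes 40% of the variance of change at r = 0.2 and 30% at r = 0.4.

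**3. What this means for a chemotherapy contrast.** Take 394 completers split 197/197. SE = √[V × (1/197 + 1/197)], and the difference detectable with 80% power is (1.960 + 0.842) × SE.

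| r | SE without | SE with | Detectable without | Detectable with |
|---|---|---|---|---|
| 0.2 | 1.529 | 1.185 | 4.28 | 3.32 |
| 0.4 | 1.325 | 1.108 | 3.71 | 3.10 |

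The Table 3 thresholds imply a 60:40 split instead (lower limits: 180 + 144 = 324 chemotherapy of 540). That gives 4.37 v 3.39 points at r = 0.2 and 3.79 v 3.17 at r = 0.4. The note above Table 3 and the table disagree on which rectal stratum is the larger. Exchanging the two strata turns 60:40 into 40:60 and leaves these figures unchanged.

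**4. Starting level.** With equal SDs the slope of change on baseline is r − 1. If the chemotherapy group's mean baseline COST differs from the other group's by D, the unadjusted contrast minus the adjusted contrast is −(1 − r)D, which is −0.8D at r = 0.2 and −0.6D at r = 0.4. The documents give no D. As an assumed example, D = −3 gives a gap of +2.4 points at r = 0.2 and +1.8 at r = 0.4.

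A simulation at r = 0.2 (4,000 runs, 197 per group, no chemotherapy effect given baseline) agrees. With D = −3 the unadjusted contrast averaged +2.38 and the adjusted one −0.01. With D = 0 both averaged about −0.01. The simulated variance ratio was 1.65 with no gap and 1.60 with the gap.

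**5. Is baseline COST always measured before exposure?** Section 4.1.4 allows registration on the day chemotherapy or radiation starts. Section 6.4.1 puts the baseline assessment after registration. Footnote 1 of the Section 10 calendar allows 14 days from registration, and for paper surveys that footnote and Section 9.2.2 tie the signing date to within 14 days of starting therapy. COST has a 7-day recall window (Section 7.1.1.1). Some baseline scores may therefore be recorded after therapy has begun, and for some the recall period may lie wholly after the start.

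**The case against.** **The list is open.** The predictors are introduced as examples, and baseline questionnaire variables could be read to include COST, since self-efficacy is likewise a separate instrument given at baseline. This stands in part: a reader might infer that the plan excludes baseline COST, and the text does not say so. The broad reading still fits poorly with Section 11.4.2.4, which lists the COST score as a financial variable separate from the baseline questionnaire variables and names 6-month FACT-G7 as an adjuster. The plan names such terms when it intends them.

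**Adjustment is a choice of question, not a correction.** This stands. A reader might infer that the unadjusted chemotherapy contrast is biased by starting level. That needs a baseline difference, for which the documents give no figure, and an assumption about how the groups would otherwise have moved. The simulation builds in no effect given baseline, so it favours the adjusted model. If the groups differ stably and would otherwise change in parallel, the unadjusted contrast is the unbiased one and the adjusted one is off by (1 − r)D. Nor can baseline COST be called a pre-exposure covariate for everyone, given the survey windows.

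**The mixed model covers the hypothesis.** Section 1.2.6 speaks of the level of burden, and Section 11.4.2.3 plans a five-visit mixed model with treatment plan and interactions, which shows baseline differences openly. It covers the question in part but does not deliver the precision gain. It treats baseline COST as an outcome and states no constraint of equal baseline means. With complete data, categorical time and a group-by-time interaction, its 12-month contrast is the unadjusted difference in mean change.

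**No between-group target exists.** Correct. The 2.5 points is the within-cohort change. Power for a 2.5-point chemotherapy contrast would borrow that figure, so the size is given here as detectable differences.

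**Conclusion.** The point holds as a gap in specification with a measurable cost in precision. On the plan's SD of 12, leaving baseline COST out means 67% (r = 0.2) or 43% (r = 0.4) more residual variance than including it. For an equal chemotherapy split this raises the detectable difference by about 1.0 point (4.28 − 3.32 = 0.96) or 0.6 points (3.71 − 3.10 = 0.61). These figures rest on the plan's assumed correlations and on no other covariates. The ratio 2/(1 + r) shrinks as r rises, and covariates correlated with baseline COST would narrow the gap.

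On starting level, the supportable statement is conditional: the two contrasts differ by 0.8D or 0.6D if the groups differ by D. A reader might go further and infer that the main result is weakened. It is not: the paired test, the 394 completers and the 563 enrolled do not depend on these regressions, which Section 11.4.1 introduces as additional. The point is worth acting on because the remedy uses data already planned for collection and removes a modelling choice that would otherwise be open at analysis.

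**What to change.** In Section 11.4.1:

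1. Name baseline COST as a covariate in the 12-month change regressions. Modelling 12-month COST on baseline COST plus the predictors is equivalent and gives the same predictor coefficients.
2. Report the unadjusted change model beside it for all predictors, including chemotherapy status and the three-level treatment status. State what each answers: the unadjusted model compares average change between the groups as they stand; the adjusted model compares 12-month COST among patients who start at the same score. Say that chemotherapy is not randomised, so the two need not agree.
3. Add a sensitivity analysis excluding patients whose baseline COST was completed after chemotherapy or radiation began, since Section 9.2.2 and footnote 1 of Section 10 allow this.

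The cost is a few sentences and one extra model run. No patients or questionnaires are added. Section 8.2.2 says survey completion dates are recorded; the team should confirm that therapy start dates are captured too, since item 3 needs both.
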